5.4 Baseline and Demographic Characteristics of the Subjects

The demographic and baseline characteristics of the subjects will be summarized for each treatment. Descriptive summaries will include number of subjects, mean, standard deviation, median, minimum and maximum for continuous parameters, frequencies and percentages for categorical parameters.

A t-test or chi-squared test, as appropriate for quantitative or categorical data, will be used to determine whether there were differences in the baseline demographic profiles of the groups. Differences were considered significant at p values <0.05 .

5.5 Efficacy and Safety Analysis for the Aims

It will be carried out as follows:

A. Antidepressant effect of NIR-TLT doses:

To compare the antidepressant effects of NIR-TLT doses, mean changes in HAM-D 17 scores (for evaluation of the Primary Assessment Criteria) and QIDS-C and CGI-S (for evaluation of the Secondary Assessment Criteria), will be performed for each dose at 3 time points (visit 1, visit 9 and visit 18) will be compared using a repeated measures ANCOVA. A significant ANCOVA interaction in mean score changes between groups will be taken as indicating that the groups have different antidepressant efficacy. If significant ANCOVA interactions are found, paired samples t-tests will be used to explore differences between scores/groups.

Both the full analysis and the analysis by intention will be performed to analyze the severity of depression at the endpoint. Patient attrition and dropout will be analyzed. The possible

Transcranial Near Infrared Laser Therapy in Subjects with Major Depressive Disorder: A Laser Dosing Study.

differences between treatment groups in dropouts will be examined with Fisher's exact test.

B. Brain electrophysiological effect of NIR-TLT doses:

To compare the effects of NIR-TLT doses on brain electrophysiology, changes in EEG spectral power in all spectral bands for each dose at 3 time points (visit 1, visit 9, and visit 18) will be compared using a repeated measures ANCOVA. A significant ANCOVA interaction in mean score changes between groups will be taken as indicating that the groups have different effects. If significant ANCOVA interactions are found, paired samples t-tests will be used to explore differences between groups.

C. Safety and tolerability of NIR-TLT doses:

To compare the safety and tolerability of NIR-TLT doses, mean changes iSAFTEE-SI scores at 3 time points (visit 1, visit 9, and visit 18) will be compared using a repeated measures ANOVA. A significant ANOVA interaction in mean score changes between groups will be taken as indicating that the NIR-TLT doses have different tolerability. If significant ANOVA interactions are found, paired samples t-tests will be used to explore differences between groups.

In addition, the frequency and severity of side effects and adverse events reported for each dose will be compared using a Fisher's exact test. The corrective actions taken by the doctors as well as the clinical judgment on the likelihood of association of the side effect/adverse event with the NIR-TLT dose will also be reported.

D. Findings visualized in the PET scan:

The analysis of the results obtained in the PET will be for exploratory purposes to study the brain metabolism of the participants, before and at the end of the study intervention in the 4 groups. Following the recommendations of Daniel et al. (Daniel, 2012), for the exploratory analysis we will work with a minimum number of 5 participants per group, with a total of 20 participants.

The results obtained in the PET will be presented in a descriptive manner.

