Study Design:	
Multi-center, randomized, sham, double-blind.
 
This trial will randomize 112 subjects into 4 equal groups: bilateral continuous wave (BCW), bilateral pulsed wave (BPW 1-2) and SHAM. All subjects, investigators (except the study statistician) and outcome assessors will be blinded to group assignments. The device operator will be aware of group assignments.
 
All subjects will receive 3 NIR-TLT sessions per week for 6 weeks. A follow-up evaluation will be performed 2 weeks after the end of the study. The treatment will follow these specifications: wavelength 830 nm; average irradiance 54.8 mW / cm²; average fluence of 65.8 J / cm² (according to the parameters used in the ELATED-2 study at MGH with the Omnilux New U device), being the total fluence delivered: 3.6 kJ (bilateral) or 1.8 kJ (unilateral), either on the subject's forehead, at or near the electroencephalography (EEG) sites F3 and F4.
 
All NIR-TLT sessions will be 429 seconds (7.15 minutes), regardless of group assignment.

Study population:	
Patients eligible to participate in the study will be diagnosed with MDD by DSM criteria (MINI). Subjects will be between 18 and 75 years of age (not yet 76 years of age) on the date of the examination.

Duration of participation:	
Research subjects will remain in the study for 8 weeks. (6-week treatment period, plus 2-week follow-up). The total duration of the study will be 24 months.

Near Infrared Transcranial Laser Therapy in Subjects with Major Depressive Disorder: A study of Dosing with Laser.

Criteria for valuation:

- **Main:** Improvement of depressive symptoms from each of the four doses of NIR-TLT. Assessed using HAMD-17, at 3 time points (visit 1, visit 9 and visit 18).
- **Secondary:** Safety and tolerability. Assessed by SAFTEE- SI (self-assessed), and collection of serious adverse events throughout the study. Safety data will be used to assess the tolerability of each of the NIR-TLT doses.
Changes in brain electrophysiology (electrical activity): Commercially available EEG devices will be used to collect data on brain electrical activity. At 3 time points (visit 1, visit 9 and visit 18).
- Changes in measurements of MDD symptom severity assessment scales:
 - Doctor Administered Scales: QIDS-C and CGI-S
 - Patient-reported scales: ASQ and SDQ

Entry Criteria:

Inclusion Criteria

1. The age of the subjects in the examination will be between 18 and 75 years (inclusive).

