The NIR-TLT delivery is expected to last no longer than 7.15 minutes (429 seconds) in total (simultaneous application to the left and right forehead). The subject will be allowed to rest for 5 minutes after NIR-TLT delivery. The skin at the application sites will be inspected again after laser application. A log will be kept with the dates of delivery of the NIR-TLT.

Near Infrared Transcranial Laser Therapy in Subjects with Major Depressive Disorder: A study of Dosing with Laser.

treatment per study subject. The use of cell phones, tablets, computers or electronic devices will not be allowed during laser administration.

[figure not shown]
During treatment visits and prior to NIR-TLT, study personnel will collect tolerability (safety) and efficacy data:

1. Safety data: SAFTEE-SI (self-assessed), C-SSRS, adverse events and concomitant medication form.
2. Efficacy data - HAMD-17.

In addition to the evaluation described above, during visits 1, 9 and 18:

Prior to the NIR-TLT study, the staff will collect primary efficacy data from metric measurements and brain electrophysiology data:

1. Efficiency data:
 - a. Doctor-administered scales (1): HAMD-17, QIDS-C and CGI-S.
 - b. Patient-Reported Scales (1): ASQ and SDQ
2. Brain Electrophysiology Data - Study personnel will conduct a first 10-minute EEG recording session, treat the patient according to their NIR-TLT group randomization, and then conduct a second 10-minute EEG recording session as soon as possible after the end of treatment, but within 15 minutes.

3. Exploratory PET scan data: A PET scan will be performed on the participants selected to be part of the research subgroup, before the first treatment visit and within 24 hours of the end of the last intervention (visit 18).

4.9.3 Follow-up visit (Post Treatments) - Week 8

Near Infrared Transcranial Laser Therapy in Subjects with Major Depressive Disorder: A study of Dosing with Laser.

The next visit will occur two weeks after the last cerebral blood flow impact visit.

Purpose: The purpose of the follow-up visit is to evaluate the long-term antidepressant effect of NIR-TLT.

Procedures: During the follow-up study, staff will collect tolerability (safety) and efficacy data:

1. Safety data: SAFTEE-SI (self-assessed), adverse events and concomitant medication form.

2. Efficiency data:

- a. Doctor-administered scales (1): HAMD-17, QIDS-C and CGI.
- b. Patient-reported scales (1): SDQ and ASQ.

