5.3 Sample Size

The sample size was determined using G Power software version 3.1, considering a calculation by double mean difference with common standard deviation, assuming a significance level of 0.05 and 90% power. The parameters used were obtained from page 7 (section "Antidepressant effect according to clinician-rated measurement") of the previous ELATED-2 study (Cassano et al., 2018), where the mean difference of the HAM-D17 score for the experimental group was -10.8 ± 7.55 and for the control group 4.4 ± 6.65 ; such data identify a double difference of 6.4 with common standard deviation of 7.091. With this information, a total sample of 112 participants is obtained, taking into consideration a 20% loss rate. Each group will have 28 participants.

With $n=112$, in 4 groups in a longitudinal design, we estimated a power of 90% to differentiate ($\alpha=0.05$) the therapeutic effect of the dose, giving an antidepressant effect and an effect variance equivalent to that obtained in participants who completed the ELATED-2 study for all groups (Cassano et al., 2018b)

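### Section 5.5 A treats the pre-treatment visit 1 HAM-D17 as a repeated outcome and names no covariate, so read literally its interaction test rests on change scores and may give up some efficiency

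*Protocol*

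**What the plan says.** Section 5.5 A sets the primary analysis: mean changes in HAM-D17, and in QIDS-C and CGI-S as secondary measures, "for each dose at 3 time points (visit 1, visit 9 and visit 18) will be compared using a repeated measures ANCOVA". The test of efficacy is the interaction: "A significant ANCOVA interaction in mean score changes between groups will be taken as indicating that the groups have different antidepressant efficacy". The follow-up is "If significant ANCOVA interactions are found, paired samples t-tests will be used to explore differences between scores/groups". No covariate is named.

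The summary in section 1 gives the same three visits for the main criterion: "Assessed using HAMD-17, at 3 time points (visit 1, visit 9 and visit 18".

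Visit 1 is pre-treatment. Section 4.9.2 states "During treatment visits and prior to NIR-TLT, study personnel will collect tolerability (safety) and efficacy data" and, for visits 1, 9 and 18, "Prior to the NIR-TLT study, the staff will collect primary efficacy data". The table of assessments in section 8 shows treatment beginning at visit 1.

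Section 5.5 C applies the same three visits to SAFTEE-SI, but those scores "will be compared using a repeated measures ANOVA".

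Section 5.3 sizes the trial on change scores, "considering a calculation by double mean difference with common standard deviation": a difference of 6.4 with SD 7.091, 90% power, significance level 0.05 with no sidedness stated, and 20% loss, giving 28 per group and 112 in total.

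**The concern.** A score taken before any treatment carries no treatment effect. Its best use is to explain variation in the later scores. When it sits among the repeated responses of an unconstrained model, the interaction compares arms on change from visit 1, which fixes the slope on baseline at 1. If the true slope differs from 1, the contrast is noisier than one that estimates the slope.

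Two things are at stake. The first is power for the primary question, using data that the trial collects anyway. The second is the handling of a chance visit 1 difference between arms of 22 to 28 people: a change score over-corrects for it when the true slope is below 1 and under-corrects when it is above 1.

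**Working it through.** **1. The plan's own figure.** Inputs from section 5.3: difference 6.4, SD of change 7.091, alpha 0.05, power 90%, 20% loss, four arms.

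- One-sided: n = 2[(1.645 + 1.282) × 7.091 / 6.4]² = 21.03, so 22 per arm. The exact t calculation also gives 22. Then 22 / 0.8 = 27.5, so 28 per arm and 112 in total. This reproduces.
- Two-sided: 26 per arm (normal) or 27 (exact t); 33 or 34 after loss; 132 or 136 in total. This does not reproduce.

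Both readings are carried below because the sidedness is not stated.

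**2. What the literal model tests.** Write the score of person i in arm k at visit j as m_j + g_kj + b·X_i + s_i + e_ij, where X_i is the visit 1 score and s_i a person effect. Subtract visit 1 from visit 18: both b·X_i and s_i cancel. The interaction contrast is therefore the difference in mean change whether or not X_i is in the model as a main effect (complete data). Adjustment needs a slope that varies by visit. If visit 1 is also a response, that slope at visit 1 is a score regressed on itself, with zero residual. The clean form takes visit 1 off the response side.

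**3. Power for one active-sham pair at visit 18, 22 per arm.** Noncentral t, with 42 degrees of freedom for change and 41 for adjusted. The correlation rho between visits 1 and 18 is not in the protocol; 0.3 to 0.7 is assumed.

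Change score: noncentrality = 6.4 / (7.091 × √(2/22)) = 2.99. Power is 83.3% two-sided and 90.3% one-sided.

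*Equal SDs at visits 1 and 18.* Variance ratio (adjusted / change) = (1 + rho)/2. Each SD = 7.091/√(2(1 − rho)).

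| rho | SD at each visit | ratio | adjusted SD | two-sided power | one-sided power |
|---|---|---|---|---|---|
| 0.3 | 5.99 | 0.65 | 5.72 | 95.2% | 97.8% |
| 0.5 | 7.09 | 0.75 | 6.14 | 92.1% | 96.0% |
| 0.7 | 9.15 | 0.85 | 6.54 | 88.7% | 93.9% |

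The gain is 5 to 12 points two-sided and 4 to 7 points one-sided.

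*Baseline SD 4.4* (ELATED-1 in section 3.1, n = 4; the only baseline SD in the protocol), SD of change held at 7.091. Solve 7.091² = 4.4² + sy² − 2·rho·4.4·sy for the visit 18 SD sy; adjusted SD = sy·√(1 − rho²).

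| rho | sy | slope | ratio | adjusted SD | two-sided power | one-sided power |
|---|---|---|---|---|---|---|
| 0.3 | 7.04 | 0.48 | 0.90 | 6.71 | 87.0% | 92.9% |
| 0.5 | 8.18 | 0.93 | 0.998 | 7.08 | 83.3% | 90.3% |
| 0.7 | 9.44 | 1.50 | 0.90 | 6.74 | 86.8% | 92.7% |

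The gain is 0 to 4 points two-sided and 0 to 3 points one-sided. It vanishes where the slope is near 1.

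**4. The omnibus test.** A simulation with four arms of 22, rho 0.5, equal SDs, all active arms at 6.4 and half that effect at visit 9 gave 78% power for the three-visit interaction, 87% for change at visit 18 and 95% for visit 18 adjusted for visit 1. Only the step from 87% to 95% is due to baseline adjustment; the step from 78% reflects the shape of the interaction test. Under no effect all three rejected in about 5% of runs.

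**5. Chance imbalance.** One standard error of the visit 1 difference is SD × √(2/22), and the change-score contrast shifts by |1 − slope| times that. Equal SDs: 1.8 to 2.8 points of imbalance, shift 0.8 to 1.3 points. Baseline SD 4.4: 1.3 points of imbalance, shift 0.1 to 0.7 points.

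**The case against.** The strongest reply is that the protocol never says baseline adjustment is excluded. Part A is called an ANCOVA and part C an ANOVA over the same visits, which suggests that some covariate is meant in part A, and a covariate list is commonly left to a statistical analysis plan. That stands: a reader might infer that the primary analysis is definitely unadjusted, and the text does not support that. It does not remove the point. The protocol itself fixes visit 1 as a response level and the interaction as the test, and a covariate added later as a main effect would leave that test unchanged. For SAFTEE-SI the stated ANOVA has no covariate.

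A baseline kept as a response is also not wrong in itself. A constrained longitudinal model with one common baseline mean reaches essentially the same precision as adjustment. This stands, and the fix allows it; the protocol does not state that constraint.

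A reader might infer that every arm comparison in the plan is a change-score test. It is not: the plan names an omnibus interaction followed by paired t-tests, and a paired test is not a between-arm comparison. The pairwise figures above therefore measure efficiency; they are not the power of the named procedure.

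Finally, the size is soft. Rho is assumed, and equal SDs imply baseline SDs of 6.0 to 9.2, while the only one in the protocol is 4.4 (from four people) and the entry thresholds on QIDS-C and CGI-S may narrow the spread. All of this stands and is why a range that includes zero is given.

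**Conclusion.** The point holds as one of efficiency and clarity in the primary analysis. Section 5.5 A lists a pre-treatment score as an outcome, tests the interaction and names no covariate. Read literally, the interaction and any arm contrast drawn from it rest on change from visit 1.

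For one active-sham pair with 22 per arm, the gain from adjusting is about 0 to 12 points of power two-sided and about 0 to 7 points one-sided. Gains above about 4 points two-sided arise here only with equal SDs at visits 1 and 18. These ranges assume rho of 0.3 to 0.7 and the section 5.3 SD of change. No case examined loses meaningful power.

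It would be tempting to call the planned comparison biased. Under randomisation a change-score comparison is unbiased and keeps its type I error, chance imbalance is already reflected in its standard error, and section 5.3 planned on that basis. The imbalance shift in step 5 is conditional on the allocation that happens to occur.

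**What to change.** In section 5.5 A, state that HAM-D17 at visits 9 and 18 is the response, that the visit 1 score and its interaction with visit are covariates, and that visit 1 is not a response. An equivalent constrained longitudinal model with a common baseline mean across arms would serve as well. State that between-arm contrasts are taken from that model. Do the same for QIDS-C, CGI-S and SAFTEE-SI, each with its own visit 1 value, and change the SAFTEE-SI label from ANOVA accordingly.

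The cost is a short rewording settled before unblinding and one or two degrees of freedom. No new data are needed and the sample size need not change.

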4.1 Study Aims

Primary Aim:

A. To evaluate and compare the effect(s) of each of the four doses of NIR-TLT on depressive symptomatology: antidepressant effect, in patients with major depressive disorder (MDD).

Hypothesis 1: Total HAM-D 17 scale scores will vary in a NIR-TLT dose-dependent manner, with BPW dose being more effective.

We also expect to be able to estimate the effect size of the antidepressant action as a function of the irradiance applied to the NIR-TLT skin, with the BPW dose being more effective.

Secondary Aims:

B. Compare safety and tolerability at each dose of NIR-TLT.

Hypothesis 2: The doses of NIR-TLT tested in this study will be safe and well tolerated by patients with MDD, as assessed by SAFTEE-SI and reports of serious adverse events. We do not anticipate dose-dependent differences in reported side effects.

C. To compare the effect(s) of each of the four doses of NIR-TLT on brain electrophysiology.

Exploratory Aim:

D. To describe the findings visualized in PET, related to the brain metabolism of the participants, before and at the end of the intervention under study.

4.2 Rationale for the use of the EXPi device:

Transcranial photobiomodulation (t-PBM) with near infrared (NIR) laser therapy has emerged as a possible antidepressant treatment in both animal models (Mohammed et al.2016; Salehpour 2016-2017; Xu et al.2017; Wu et al.2012), and in human studies (Cassano 2015- 2017; Caldieraro et al.2018) t-PBM. NIR appears to increase brain metabolism (by activating the cytochrome C oxidase in the mitochondria), to increase neuroplasticity and to modulate the

Near Infrared Transcranial Laser Therapy in Subjects with Major Depressive Disorder: A study of Dosing with Laser.

endogenous opioids, while decreasing inflammation and oxidative stress. (Chung et. al. 2012; Yu et. al. 1997; Oron et al. 2007, Mochizuki et al. 2002) t-PBM penetrates deep into the cerebral cortex, modulates cortical excitability, and improves cerebral perfusion and oxygenation. The safety of t-PBM has been studied in a sample of 1410 acute stroke patients, with no significant difference in adverse event rates between t-PBM and sham exposure. (Hacke et al. 2014; Lamp et al. 2007, Zivin et al. 2009) Uncontrolled studies suggest an antidepressant effect of t-PBM in subjects suffering from MDD (Cassano 2015-2017; Caldieraro et al. 2018).

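### The primary conclusion rests on a global group-by-visit interaction that fixes no visit and no comparison with sham, and its follow-up test cannot compare arms

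*Protocol*

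**What the plan says.** The Summary of the Study gives the main criterion as improvement in depressive symptoms, "Assessed using HAMD-17, at 3 time points (visit 1, visit 9 and visit 18"), without singling out a visit. The primary hypothesis in Section 4.1 is directional across doses: "Total HAM-D 17 scale scores will vary in a NIR-TLT dose-dependent manner, with BPW dose being more effective".

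Section 5.5 A compares mean changes in HAM-D17 by repeated-measures ANCOVA, "for each dose at 3 time points (visit 1, visit 9 and visit 18"). It then fixes how the result is read: "A significant ANCOVA interaction in mean score changes between groups will be taken as indicating that the groups have different antidepressant efficacy". The next step is conditional: "If significant ANCOVA interactions are found, paired samples t-tests will be used to explore differences between scores/groups". A later sentence mentions severity at the endpoint in two analysis sets, but gives no test, visit or comparator. No covariate is named for the ANCOVA.

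Section 5.3 sizes the trial on a two-group difference in mean change, "assuming a significance level of 0.05 and 90% power"; "such data identify a double difference of 6.4 with common standard deviation of 7.091". It then states, for the 112 participants "in 4 groups in a longitudinal design, we estimated a power of 90% to differentiate" the therapeutic effect of the dose.

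**The concern.** The trial is sham-controlled, with three active arms and one sham arm. The reader will want to know whether a given dose improves HAM-D17 more than sham at the end of the six weeks of treatment. The stated rule does not ask that. A global interaction is significant for any departure from parallel profiles: at visit 9 or visit 18, between an active arm and sham, or between two active arms.

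The follow-up step does not close the gap. A paired-samples t-test compares two scores from the same person. It can describe change within an arm, but it is not a valid test between independent arms. A trial that follows Section 5.5 A exactly can pass its gate and still have no valid test of any dose against sham.

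Two further points follow. The 90% power in Section 5.3 belongs to another test. And because the text says ANCOVA without naming the covariate, visit 1 could be taken as covariate only, with visits 9 and 18 as the repeated outcomes. The interaction would then test only whether the arms changed differently between visits 9 and 18.

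**Working it through.** **Inputs.** Difference 6.4, SD of change 7.091, alpha 0.05, power 90%, 20% loss, 28 per arm, 112 in total (Section 5.3). Allocation 1:1:1:1 (Section 4.4.1). Assumed, because the protocol gives no figures: within-person correlation (0.3 to 0.7) and the size of the effect at visit 9.

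**Step 1: the protocol's own figure.** For two means, n per arm = 2(z_α + z_β)² × (7.091/6.4)².
- One-sided 0.05: 2 × (1.645 + 1.282)² × (7.091/6.4)² = 21.03, so 22. Then 22/0.8 = 27.5, so 28, and 28 × 4 = 112. This reproduces the plan.
- Two-sided 0.05: 25.8, so 26 (27 by exact t), or 33-34 per arm after loss and 132-136 in total. This does not reproduce it.

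So 112 comes from one pairwise comparison of mean change, not from a four-arm, three-visit interaction.

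**Step 2: the interaction over visits 1, 9 and 18.** Under compound symmetry the error variance is half the variance of a change: 7.091²/2 = 25.14, whatever the correlation. With the same effect in all three active arms, the group term is 3 × (1/4)² + (3/4)² = 0.75. The noncentrality is λ = n × 0.75 × S/25.14, where S is the sum of squares of the active-arm effect about its mean over the three visits. With n = 22, the F test has 6 and 168 degrees of freedom.

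| Effect at visits 1, 9, 18 | S | λ | P(significant) |
|---|---|---|---|
| 0, 3.2, 6.4 (gradual) | 20.48 | 13.44 | 78% |
| 0, 6.4, 6.4 (full by visit 9, kept) | 27.31 | 17.92 | 90% |
| 0, 6.4, 0 (gone by visit 18) | 27.31 | 17.92 | 90% |

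The last two rows have the same noncentrality, so in this setting the test is exactly as likely to fire for an effect that has gone as for one that is kept. Simulations at 22 per arm agree: 89-90% for the effect that has gone, 77-81% for the gradual effect and 89-91% for the kept effect. If the SD grows over visits (4.4, 6.2, 7.03), power for the gradual effect is 84-85%, still below 90%.

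**Step 3: visit 1 as covariate only.** The interaction then tests the arm effect on the change from visit 9 to visit 18, with λ = 22 × 0.75 × δ²/7.091² on 3 and 83 degrees of freedom, where δ is that change in the effect.
- Kept effect: δ = 0, power 5%.
- Gradual effect: δ = 3.2, λ = 3.36, power 29% (up to 47% with growing SD).
- Gone by visit 18: δ = 6.4 in size, λ = 13.44, significant in 87%.

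**Step 4: visit-18 contrast with sham, adjusted for visit 1.** The residual variance is 7.091² × (1 + ρ)/2. The residual SD is 5.717 at ρ = 0.3 and 6.538 at ρ = 0.7. The noncentrality 6.4/√(2 × variance/22) is 3.71 and 3.25.
- A given arm, two-sided 0.05/3: 90% at ρ = 0.3 and 79% at ρ = 0.7. Across the Bonferroni and Dunnett simulations the range is 77-91%.
- At least one of three arms, all three effective: 94-98%.
- Effect gone by visit 18: any arm significant in about 4-5%.

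**The case against.** The fair reply is that the rule says only that the groups have different efficacy, that the main criterion is defined over three visits, and that the aim is to compare four groups. On those terms an arm difference at visit 9 is a real difference, and the 89-90% is not a type I error. That stands. The scenario is also a stress case: the protocol gives no reason to expect a 6.4-point effect to vanish while treatment continues.

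Three stronger readings are tempting, and the documents do not support them.
- A reader might infer that the rule declares a dose efficacious. It does not; it declares that groups differ. The defect is that nothing valid follows to link a dose to sham.
- A reader might infer that the gate loses power in general, for example by setting 77-81% against 94-98%. The latter is the chance that at least one arm succeeds when all three work; for a given arm it is 77-91%. It also benefits from baseline adjustment. When the effect is full by visit 9, the gate shows no consistent loss.
- A reader might infer that anyone missing a visit is dropped. Section 5.5 does not say so. It plans an analysis by intention, and Section 4.19.1 collects HAM-D17 at an exit visit. Handling of missing data may sit in the unseen analysis plan.

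The covariate-only reading also departs from the three visits that Section 5.5 lists. The 5% figure therefore shows an ambiguity to close, not a stated error.

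The missing sham contrast cannot be left to the analysis plan, because the protocol already fixes a different decision rule.

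**Conclusion.** The point holds. Section 5.5 A fixes a primary rule without a primary visit or a sham contrast, and with a follow-up test that is invalid between arms. It cannot show which dose beats sham at the end of treatment, and it is not the comparison that produced 112.

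At 22 evaluable per arm it is significant in about 89-90% of trials when arms differ only at visit 9, against 4-5% for visit-18 contrasts. For a gradual effect its power is about 77-81%, short of the stated 90%; for an effect full by visit 9 it is 89-91%. Power loss is thus possible, not general. Under the covariate-only reading, power is about 5% for a kept effect and 29% for a gradual one.

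These figures assume a common 6.4-point effect in all active arms, an SD of change of 7.091, compound symmetry with correlation 0.3 to 0.7, and the visit-9 effects shown. The structural defect depends on none of these.

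**What to change.** In Section 5.5 A:
1. Make the primary test each active arm versus sham in HAM-D17 at visit 18. Estimate it from a mixed model for repeated measures on visits 9 and 18, with visit-1 HAM-D17 as covariate.
2. Control the three comparisons by Dunnett or Holm.
3. Delete the paired t-tests between arms.
4. Report the group-by-visit interaction as descriptive. State the role of visit 1, so that the covariate-only interaction is excluded as a decision rule.

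In the Summary of the Study, name visit 18 as the primary time point. In Section 5.3, restate power for the new primary test and give its sidedness.

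This needs wording only; HAM-D17 is already collected at visits 1, 9 and 18 (Section 8). The cost is that multiplicity-adjusted power for a given arm is about 77-91%, so the present 90% cannot simply be carried over. The 94-98% should be quoted only as power for at least one arm when all three work.
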